5.7 Restrictions

5.7.1 Prior Therapy

Subjects must meet inclusion and exclusion criteria outlined in Sections 4.2 and Section 4.3, respectively.

5.7.2 Fluid and Food Intake

In general, subjects should follow their normal diet and fluid intake through the course of the study and maintain a consistency regarding when meals and study drug are taken.

5.7.3 Patient Activity Restrictions

Subjects should continue their normal activities of daily living during the study.

5.8 Treatment Compliance

Subjects should be reminded to return all unused study drug at each study visit, as well as the empty packages of study drug used. The study coordinator or designee will document the unused study drug and verify that the quantity is consistent with the intended dosing schedule. Based on drug accountability with regard to the subject's prescribed dosage regimen, throughout the study, if non-compliance is suspected, the clinical site personnel will re-educate the subject on the importance of proper adherence to the prescribed dosing. Continued noncompliance may lead to termination of the subject from the study after consultation between the investigator and the sponsor.

5.9 Packaging and Labeling

The sponsor will supply study drug for the study. Esuberaprost sodium tablets (15 µg) and matching placebo will be mounted in identical child resistant Dose-Pak[®] wallet cards. At the Enrollment Visit, each subject in the study will be assigned via the IRT, a study drug "transition kit". The subject-specific "transition kit" will contain 4 weekly wallet cards, one for each of the first 4 weeks of the study. Each designated wallet card will provide the appropriate daily dosing for the Weeks 1 through 4; they will contain 8 tablets per day, 2 for each of the 4 doses to be taken each day). The "transition kit" will contain the appropriate blinded treatment of either 2 tablets of esuberaprost per dose or 1 tablet of placebo and 1 tablet of esuberaprost per dose (for the first 2 weeks for former placebo subjects).

At the Week 4 Visit and at Quarterly Visits thereafter, the subject will be issued via the IRT bulk dosing cards of esuberaprost tablets to provide an adequate supply of study drug for continued use until the subject's next scheduled study visit.

Study drug will be labeled in accordance with all applicable local regulations to include at least the following information: the sponsor's name and address, protocol number, contents of the Dose Pak[®] wallet cards, lot number, directions for use, storage conditions, and FDA caution statement.

5.10 Storage and Accountability

Study drug should be stored at approximately 25°C (77°F). Excursions between 15°C and 30°C (59-86 °F) that are experienced in pharmacies, hospitals, and warehouses are acceptable [USP Controlled Room Temperature, 2008]. Study drug should be protected from light and moisture and should not be frozen or exposed to heat. At the clinical site, study drug will be stored in a securely locked cabinet or enclosure. Access should be strictly limited to the investigators and their designees.

The sponsor or designee is responsible for assuring that the quantity and quality of the study drug is adequate for the duration of the study.

Study drug should be used in accordance with the protocol, under the supervision of the investigator or designee (e.g., the clinical site pharmacist or other personnel trained to store and dispense investigational drugs). The investigator or designee must agree to supply study drug only to subjects enrolled in the study. Subjects must be given the study drug corresponding to their own randomization number.

The study coordinator, pharmacist or appropriate personnel at the investigational clinical site will deliver and retrieve study drug assigned to the subjects at each study visit. Subjects will be instructed to return all study drug, including all empty or partially used packages, to the appropriate study personnel on an ongoing basis.

5.11 Investigational Product Retention at Study Site

The investigator or designee is responsible for taking an inventory of each shipment of study drug received and comparing it with the accompanying packing list. The investigator or designee will verify the accuracy of the information on the packing list, sign and date the acknowledgement of receipt, retain a copy in the study file, and acknowledge receipt of the shipment to the sponsor via the IRT system.

The investigator is responsible for study drug accountability and reconciliation overall and on a per subject basis. Drug accountability records are to be maintained during the study and these records include:

- the amount of study drug received from the sponsor,
- the study drug kit numbers,
- the amount dispensed to each subject,
- the dates of drug inventory movement,
- the initials of the person responsible for each drug inventory entry,
- the date and amount of unused drug returned from each subject,
- the amount of unused drug on site, available for future subject assignment

At each study visit, site personnel should assess drug dispensed, drug returned (including all empty or partially used wallets), and dosing information to confirm drug accountability and compliance. If any study drug was lost or damaged, its disposition should be documented in the subject's source documents as well as the in the IRT system. Accurate recording of study drug administration (including dispensing and dosing) will also be made in the appropriate section of the source documents and IRT system. Once a representative from the sponsor has confirmed drug accountability for each subject, all used and unused study drug will either be returned to the sponsor (or designee) per the sponsor's (or designee's) written instructions, or be destroyed by the site and destruction information entered in the IRT system.

6 STUDY PROCEDURES

All relevant data captured at the BPS-314d-MR-PAH-302 EOS Visit will be entered in the Enrollment Visit CRFs, as required by this protocol.

6.1 Informed Consent

The investigator and/or designee will explain study procedures to potential subjects prior to participation in this study. Those who agree to participate will sign and date the IRB or IEC approved ICF after reading the document and after the investigator has answered any questions about the study. The investigator and/or designee will also sign and date the ICF. Subjects will be given a copy of the ICF.

In the US only, for the optional collection of blood sample for future biomedical research (see Section 6.9.2), a separate ICF must be signed by the US subjects agreeing to participate. A subject's participation in the OLE study will in no way be affected if he/she declines consent for the optional future biomedical research.

In order to provide seamless continuation of esuberaprost sodium tablet treatment, subjects must provide informed consent for this OLE study on or prior to the EOS Visit for the BPS-314d-MR-PAH-302 study.

6.2 Medical History

Medical and surgical history that was collected from each subject during the randomized, controlled, BPS-314d-MR-PAH-302 study will be used for this study. No repeat entry of data already entered in BPS-314d-MR-PAH-302 database will be necessary.

Prescription and/or nonprescription medications at the Enrollment Visit will be assessed and entered in the concomitant medications CRF to enable tracking of any changes to medications which occur during the study. Nonprescription medications include vitamins and herbal preparations.

6.3 Physical Examination

A physical examination will be conducted by a qualified study clinician as outlined in the Schedule of Events ([Appendix 1](#)). Physical findings within the following categories will be assessed as relevant: mental status/mood; neurological; head, eyes, ears, nose, and throat; cardiovascular; respiratory; abdomen; gastrointestinal; musculoskeletal; hair and skin; and extremities. Any values judged by the investigator to be clinically significant abnormal changes after subject's first dose of study treatment as part of the OLE study should be recorded on the Adverse Event CRF as an AE.

6.4 Vital Signs

Vital signs will be measured at all scheduled study visits. Subject height will be recorded at the Enrollment Visit and weight will be recorded at each study visit. Systolic and diastolic blood

pressure, heart rate, and temperature will be measured after a seated rest per the site's standard procedures.

Any values judged by the investigator to be clinically significant abnormal changes after subject's first dose of study treatment as part of the OLE study should also be recorded on the Adverse Event CRF as an AE.

6.5 Electrocardiogram Assessment

Twelve-lead electrocardiograms (ECGs) will be recorded following rest per the site's standard procedure in the semi-recumbent position at each study visit.

Recordings will include lead II as a rhythm strip and contain at least 5 QRS complexes. ECG parameters collected include heart rate, as well as PR interval, QT interval, QTc interval, QRS duration, and any clinically significant abnormalities.

Any values judged by the investigator to be clinically significant abnormal changes after the subject's first dose of study treatment as part of the OLE study should also be recorded on the Adverse Event CRF as an AE.

6.6 Clinical Laboratory Tests

6.6.1 Laboratory Parameters

Blood and urine specimens for the measurement and evaluation of serum chemistry, hematology, coagulation, urinalysis, and N-terminal pro-Brain Natriuretic Peptide (NT-pro-BNP) will be collected at each study visit.

Subjects will be in a seated or supine position during blood collection. Clinical laboratory parameters will include those presented in [Table 2](#). Blood samples will be sent by the site to a certified central laboratory for analysis. Results will be forwarded to the sites and electronically transferred into the study database.

Any laboratory test result that the investigator considers clinically significant may be repeated to rule out laboratory error. For tests where a persistent abnormality is considered to be drug related, repeat analyses will be performed until the cause is determined and either a return to normality occurs or the investigator deems the abnormality to be of no clinical significance. Any values judged by the investigator to be clinically significant abnormal changes after the subject's first dose of study treatment as part of the OLE study should also be recorded on the Adverse Event CRF as an AE.

Table 2. List of Laboratory Tests


Hematology:
 
 - Hematocrit (Hct) - Hemoglobin (Hgb) - Mean corpuscular hemoglobin (MCH) - Mean corpuscular hemoglobin concentration (MCHC) - Mean corpuscular volume (MCV) - Platelet count - Red blood cell (RBC) count - White blood cell (WBC) count with differential 
 - Neutrophils (Total %) - Lymphocytes (Total %) - Monocytes (Total %) - Eosinophils (Total %) - Basophils (Total %) 
Urinalysis:
 
 - Appearance - Bilirubin - Color - Glucose - Ketones - Microscopic examination of sediment - Nitrite - Occult blood - pH - Protein - Specific gravity - Urobilinogen 	
Serum Chemistry:
 
 - Albumin (ALB) - Alkaline phosphatase (ALK-P) - Alanine aminotransferase (ALT; SGPT) - Aspartate aminotransferase (AST; SGOT) - Blood urea nitrogen (BUN) - Calcium (Ca) - Carbon dioxide (CO₂) - Chloride (Cl) - Creatinine - Gamma-glutamyl transferase (GGT) - Globulin - Glucose - Lactate dehydrogenase (LDH) - Phosphorus - Potassium (K) - Sodium (Na) - Total bilirubin - Direct bilirubin - Total protein - Uric acid - NT-pro-BNP 
Coagulation:
 
 - Prothrombin time (PT) - Activated partial thromboplastin time (PTT) 
Pregnancy test:
 
 - Urine pregnancy test at Enrollment Visit - Serum pregnancy test at all post-Enrollment study visits
---	--

6.6.2 Pregnancy Test

A positive pregnancy test will exclude the subject from participation in the study. For females of childbearing potential, a urine pregnancy test will be taken at the Enrollment Visit, and a serum test will be performed at all post-Enrollment study visits.

6.6.3 Sample Collection, Storage, and Shipping

Analysis of laboratory specimens listed in [Table 2](#) will be performed by a certified central laboratory. Detailed handling and shipping procedures will be provided in the laboratory manual to site personnel. All laboratory data results will be maintained as source documentation in the subject medical record.

6.7 Dispensing Study Drug

Study site personnel will dispense appropriate supplies of esuberaprost (and placebo during the transition period) to subjects at each study visit. Subjects will be instructed to return all esuberaprost, including empty or partially used packages, to the appropriate study personnel at post-Enrollment site visits.

Esuberaprost dosing during the study will be recorded in the appropriate CRF. Detailed study drug disposition records will be maintained as previously described (Section 5.10).

6.8 Efficacy Assessments

Efficacy will be assessed as a secondary objective by continuing to evaluate the efficacy parameters from the BPS-314d-MR-PAH-302 study. The 6-Minute Walk Distance (6MWD), the Borg Dyspnea Score, World Health Organization (WHO) Functional Class (FC), and NT-pro-BNP, will be assessed at each post-Enrollment study visit.

6.8.1 Six-Minute Walk Distance

The 6-minute walk test (6MWT), which is designed to evaluate exercise capacity associated with carrying out activities of daily living, will be performed to evaluate potential treatment effects on exercise capacity at each post-Enrollment study visit.

[Appendix 2](#) presents the standardized procedures for administration of the 6MWT.

If a subject is assessed for the 6MWT while using oxygen therapy, the use of oxygen should be recorded on the CRF. Oxygen use for all future 6MWTs should be conducted in accordance with the Investigator's clinical judgement.

6.8.2 Borg Dyspnea Score

The modified 0-10 category-ratio Borg scale is one in which the subjects rate the maximum level of dyspnea they experienced during the 6MWT. Scores range from 0 (for the best condition) and 10 (for the worst condition) with nonlinear spacing of verbal descriptors of severity corresponding to specific numbers. Subjects may choose the number or the verbal descriptor to reflect presumed ratio properties of sensation or symptom intensity. [Appendix 3](#) presents the standardized administration details for the Borg Dyspnea Score procedures the clinical site personnel should use. Each subject will provide a rating of dyspnea immediately following the 6MWT.

6.8.3 WHO Functional Class

At the Enrollment Visit the investigator will classify the subjects for PAH severity using the WHO FC. Assessment for WHO FC for PAH should be made at each post-Enrollment study visit. See [Appendix 4](#) for categories.

6.9 Other Assessments

6.9.1 Quality of Life Assessment

Quality of life will be assessed for all subjects at Enrollment and Month 6 using the PRO instrument, emPHasis-10. Refer to [Appendix 6](#) for details.

6.9.2 Future Biomedical Research

For those subjects in the US who choose to participate and provide a separate informed consent, blood samples will be collected at Enrollment (prior to initial esuberaprost dosing in the OLE study) and at Month 3 Visits for future biomedical research (e.g., biomarker and genomic analysis). Biomarker and genomic samples will be collected pre-dose at the Enrollment Visit and a follow-up biomarker sample at any point during the visit for Month 3. Details about sample handling will be provided in Study Procedures Manual.

6.10 Adverse Events Assessments

6.10.1 Performing Adverse Events Assessments

The clinical site personnel will monitor all AEs throughout the study, from the time of the subject's signed informed consent for this OLE study until the end of the subject's study participation. At all study site visits and during phone calls to the subject by clinical site personnel, reports of AEs will be elicited by a verbal probe ("How are you feeling?"). Subjects will be encouraged to contact the site to report an AE at any time. Appropriate measures, including medical intervention and/or procedures, will be instituted if clinically indicated at the discretion of the investigator.

All AEs occurring during the study, including AEs that are on-going at the EOS Visit from the BPS-314d-MR-PAH-302 study, must be documented in the subject's source documents and in the CRFs for AEs. For each AE, the investigator will evaluate the intensity and seriousness, as well as the relationship to esuberaprost. Information relating to the AE, such as onset and cessation date and times, escalation, frequency, action taken, and outcome will also be documented (see [Appendix 5](#)) in the CRFs for AEs. Where possible, AEs should be recorded using standard medical terminology. If several signs or symptoms are clearly related to a medically defined diagnosis or syndrome, the diagnosis or syndrome should be recorded on the CRFs for AEs, not the individual signs and symptoms.

6.10.2 Timing

Subjects with AEs that are ongoing at the subject's last study visit must be followed until resolution or for 30 days after the subject's last study visit, whichever comes first. Adverse events that are reported during the 7 days following the subject's last study visit will be recorded in the CRFs for AEs and followed until resolution or for up to the 30 days after the subject's last study visit, whichever comes first. All AEs that are ongoing after follow-up for 30 days will be recorded as ongoing in the CRF. The investigator is expected to provide or arrange appropriate supportive care for any subject with ongoing AE(s).

Serious adverse events (SAEs) should be followed until they resolve or the event or their sequelae stabilize. Supplemental measurements and/or evaluations may be necessary to investigate fully the nature and/or causality of an AE or SAE. Such supplementary assessments may include additional laboratory tests, diagnostic procedures, or consultation with other healthcare professionals. The CRFs for AEs should be updated with any new or additional information as appropriate.

If the subject reports or the investigator learns of any new SAE that occurs up to 30 days after the subject's last study visit, the clinical site personnel will ensure that these data are recorded on the AE CRF and the SAE Report Form completed and submitted accordingly.

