3.3 Study Duration and Dates

This study is expected to continue until the first of any of the following are reached: the study drug is commercially available, the sponsor discontinues the study, or the sponsor offers enrollment in another study.

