5.2.1 Selection and Timing of Dose for Each Patient

At the Enrollment Visit in this study, subjects will begin a blinded transition from the BPS-314d-MR-PAH-302 study to the OLE study over a 4-week period. The first dose for all subjects in this OLE study will be 2 tablets. During this blinded transition period, those subjects who are on active study drug in the BPS-314d-MR-PAH-302 study will continue with blinded active study drug QID; those subjects on placebo in BPS-314d-MR-PAH-302 will receive one active tablet and one placebo tablet QID (blinded) during the first 2 weeks and increase to 2 active tablets QID (blinded) thereafter. After the first dose, the investigator may adjust the dose as medically warranted. The maximum dose for this study is 30 µg QID with a minimum accepted dose as 15 µg QID.

At the Week 4 Visit, subjects will receive esuberaprost sodium tablets in bulk dosing cards, which will be the study drug packaging and configuration provided for the remainder of the study (see Section 5.9).

At the conclusion of the study (see Section 3.3), or if a subject discontinues the study prematurely, subjects will return to the clinic for an EOS Visit. If necessary, the subject should be weaned off study drug at a maximum decrement of 1 tablet QID and a minimum decrement of 1 tablet QID per week (scenarios provided in Table 1). However, the transition strategy off study drug is at the Investigator discretion as medically warranted.

Table 1. Down-Titration of Esuberaprost

Maximum Scenario		Minimum Scenario	
Day 1	2 tablets QID	Week 1	2 tablets QID
Day 2	1 tablet QID	Week 2	1 tablet QID
Day 3	No tablets	Week 3	No tablets

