6.10.8 Treatment-Emergent Adverse Events

Treatment-emergent AEs will be defined as events that are newly occurring or worsening following treatment with esuberaprost at the Enrollment Visit.

The most frequently reported treatment-emergent adverse events (TEAEs; $\geq 10\%$) for esuberaprost tablets are headache, nausea, dyspnea, dizziness, diarrhea, upper respiratory tract infection, cough, fatigue, sinusitis, flushing, worsening PAH, urinary tract infection, and vomiting.

Prostacyclins, as a class, may increase the risk of bleeding and hypotension.

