6.12 Removal of Patients from the Trial or Study Drug

A subject may voluntarily withdraw or be withdrawn from study at any time for reasons including, but not limited to the following:

- The subject wishes to withdraw from further participation;
- A serious or life-threatening adverse event occurs;

- The subject is noncompliant with the requirements of the protocol, or;
- The subject's behavior is likely to undermine the validity of his/her results.

If a subject is discontinued from the study, the investigator must provide an explanation in the source documents and record the reason for termination in the appropriate CRF for that subject. If necessary, the subject should be weaned off study drug at a maximum decrement of 1 tablet QID and a minimum decrement of 1 tablet QID per week (scenarios provided in [Table 1](#)). The transition strategy off of study drug is at the investigator discretion as medically warranted. If discontinuation from study drug is within the first 4 weeks of the OLE study, the down-titration will occur in a blinded fashion. The investigator should make every effort to perform all scheduled evaluations prior to withdrawal of study drug. A subject who discontinues because of an AE will be followed until the investigator determines the AE has resolved, is no longer considered clinically significant, has been determined to be stable and unlikely to further evolve, or for 30 days, whichever comes first.

If a subject fails to return to the clinical site, the clinical site staff must document at least two phone calls were made to the subject, and a registered letter was sent to them requesting return of study drug and contacting study personnel before considering them lost to follow-up.

The study may be stopped at any time if continuation of the study represents a serious medical risk to the subjects. Such risk may include, but is not limited to, the presence of serious, life-threatening, or fatal AEs or AEs that are unacceptable in nature, severity, or frequency. The sponsor reserves the right to discontinue the study for any reason at any time.

When a subject withdraws from the study, the site should enter the reason for discontinuation into the subject's source documents and in the subject's CRF.

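### The 7-day window for recording new AEs runs from the last study visit, not the last dose, so a slow taper after the End-of-Study Visit can leave 0 to 7 dosing days outside it

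*Combined protocol and SAP*

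**What the plan says.** Section 6.10.2 sets the rules for AEs after a subject's last visit. For AEs in general: "Adverse events that are reported during the 7 days following the subject's last study visit will be recorded in the CRFs for AEs". For serious events the window is longer and covers "any new SAE that occurs up to 30 days after the subject's last study visit". AEs already ongoing at the last visit are followed to resolution or for 30 days. Each of these clocks starts at the last study visit; none mentions the last dose.

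Section 5.2.1 gives the order of events at the end: "subjects will return to the clinic for an EOS Visit. If necessary, the subject should be weaned off study drug". Section 3.1 uses the same order, with taper instructions following the EOS Visit. Table 1 shows a fast scenario (2 tablets QID on Day 1, 1 tablet on Day 2, none on Day 3) and a slow one (2 tablets QID in Week 1, 1 tablet in Week 2, none in Week 3). The choice is left to the investigator.

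Section 6.10.1 has AEs monitored "from the time of the subject's signed informed consent for this OLE study until the end of the subject's study participation". The end of participation is not defined. Appendix 1 footnote c ties the Study Termination CRF to the EOS Visit. Neither Section 7 nor Appendix 1 schedules any contact after EOS; the calls in Section 7.2 fall between Enrollment and Week 4.

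**The concern.** The primary safety endpoint in the Synopsis is the incidence and severity of AEs under long-term exposure. Section 6.10.8 defines treatment-emergent AEs as "events that are newly occurring or worsening following treatment with esuberaprost at the Enrollment Visit", with no end date. A new AE that starts during the taper therefore meets the definition. If the taper runs past day 7 after the last visit, though, Section 6.10.2 no longer guarantees that the event is recorded.

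The general rule also depends on when an AE is reported, whereas the SAE rule depends on when it occurs. With no scheduled contact after EOS, nothing prompts an early report. Sites that read Section 6.10.1 broadly and sites that read Section 6.10.2 narrowly could record different events over the same days. The SAP that Section 9 promises could later set an end date for treatment emergence, but it could not recover events that were never entered.

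**Working it through.** **Reproducing Table 1.** Section 5.2.1 starts from 2 tablets QID and removes 1 tablet per step, which gives 2 steps with drug. Daily steps: 2 × 1 = 2 dosing days. Weekly steps: 2 × 7 = 14 dosing days, none from Week 3. Both match the table.

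**Inputs from the documents.** AE recording window: 7 days from the last visit (6.10.2). New-SAE window: 30 days from the last visit (6.10.2). Slow scenario: 7 days at 2 tablets QID, then 7 days at 1 tablet QID (Table 1). Tablet strength 15 µg; accepted doses 15 to 30 µg QID (5.2.1).

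**Assumptions, because the documents do not say.** Call the EOS Visit day 0 and treat it as the last study visit. Let f be the number of days of the 2-tablet week that fall after EOS, from 0 to 7. Post-visit dosing is counted from day 0 or from day 1; both are shown.

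**Formulas**, with L the day of the last dose and U the dosing days after day 7:
- counting from day 0: L = f + 6, U = max(0, f − 1)
- counting from day 1: L = f + 7, U = f

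| Case | L | U |
|---|---|---|
| Slow, from 2 tablets, f = 7 | 13 or 14 | 6 or 7 |
| Slow, from 2 tablets, f = 3 | 9 or 10 | 2 or 3 |
| Slow, from 2 tablets, f = 0 | 6 or 7 | 0 |
| Slow, from 1 tablet (7 dosing days) | 6 or 7 | 0 |
| Fast, from 2 tablets (2 dosing days) | 1 or 2 | 0 |

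The range over all f is 0 to 7 days. In the longest case, 6/14 = 43% or 7/14 = 50% of the taper days lie outside the window, which is 6 × 4 = 24 or 7 × 4 = 28 doses of one tablet.

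**SAEs.** Even in the longest case, cover extends 30 − 14 = 16 or 30 − 13 = 17 days past the last dose. There is no gap for new SAEs.

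**Does dosing continue after EOS?** The sections point both ways.
- For: the order in Sections 3.1 and 5.2.1, and the first part of Section 6.7, "Study site personnel will dispense appropriate supplies of esuberaprost (and placebo during the transition period) to subjects at each study visit".
- Against: Section 6.7 also has subjects return all esuberaprost at post-Enrollment visits. Section 7.5 lists no drug supply at EOS, although Sections 7.1, 7.3, 7.4 and 7.6 list it for every other type of visit. Section 5.9 issues bulk cards at Week 4 and Quarterly Visits to last until the next scheduled visit.
- Uninformative: the Study drug row of Appendix 1 is marked under EOS, but also under Phone calls, where nothing can be dispensed.
- Ambiguous: Section 6.12 says "The investigator should make every effort to perform all scheduled evaluations prior to withdrawal of study drug", without saying whether withdrawal means the start of the taper or the last tablet.

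**The case against.** The strongest reply is that the 7-day sentence includes events and does not exclude any. It says that AEs reported in those days are recorded; it does not say that later reports are refused. Section 6.10.1 asks for all AEs during the study to be documented and encourages subjects to report at any time. Read together, Section 6.10.1 covers participation and Section 6.10.2 adds a tail. This stands to a large extent. A reader might infer that the protocol orders sites to stop recording at day 7, and the text does not say so. What remains is that recording past day 7 depends on an end of participation that no section defines.

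Second, dosing after EOS is not established. A reader might infer from Section 6.7 or Appendix 1 that drug is supplied at EOS for the taper, but the evidence above is mixed. A post-EOS taper is a fair reading of Sections 3.1 and 5.2.1, not a settled fact.

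Third, the exposure is limited. Weaning happens only where needed and is at the investigator's discretion. The study ends at the first of three events, "the study drug is commercially available, the sponsor discontinues the study, or the sponsor offers enrollment in another study", and the first and last of these may make weaning unnecessary. Subjects who discontinue because of an AE are followed for up to 30 days (6.12). A later Unscheduled Visit would move the anchor. All analyses are descriptive (9.1). These points stand and keep the matter small.

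**Conclusion.** The point holds in a limited form. Section 6.10.2 guarantees recording of newly reported AEs only for 7 days after the last study visit. If the slow scenario from 2 tablets QID follows EOS, 0 to 7 dosing days fall beyond that guarantee.

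The 6 or 7 day result is the worst case under Table 1. It needs a subject on 2 tablets QID, a taper judged necessary, the slow scenario, the whole 14-day schedule after EOS, and no later visit. Because the investigator may depart from Table 1, 7 is not a protocol-wide ceiling. It would also be wrong to infer that about half of taper AEs are lost: 43 to 50% is a share of taper days in that one case, not of events, and the taper is a short part of long-term exposure.

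Only new non-serious AEs are at issue. The likely consequence is a small undercount in descriptive AE tables. The number of subjects affected cannot be derived from the documents. This is a cheap improvement, not a threat to the study's conclusions.

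**What to change.** In Section 6.10.2, run the existing 7-day recording window from the later of the last study visit and the last dose of study drug, including any down-titration. No dosing day can then fall after the window. The cut-off, now day 7, becomes:
- full slow schedule after EOS: 13 + 7 = day 20, or 14 + 7 = day 21
- only the 1-tablet week after EOS: 6 + 7 = day 13, or 7 + 7 = day 14
- fast scenario: 1 + 7 = day 8, or 2 + 7 = day 9

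Reconcile Sections 5.2.1, 6.7, 6.10.1, 6.10.2, 6.12 and 7.5 on three matters: the order of EOS Visit and taper, whether drug is supplied at EOS, and when study participation ends.

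Optionally, add one call at the end of a post-EOS taper to record AEs and the final dose, which Appendix 1 footnote h asks to have logged. The taper, the SAE window and the 30-day follow-up limit stay as they are.

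The cost is a wording change and a slightly later close-out for subjects who taper after EOS, plus one call each if that option is taken. Under the unchanged 30-day limit, an AE first reported at the latest cut-off would have 30 − 21 = 9 or 30 − 20 = 10 days of follow-up left.
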